2.1 Assessment and management of risk

This study involves vaccinating pregnant women with COVID-19 vaccines within a time period in the UK. There is a small risk of adverse reaction to any vaccine, but this risk is low and is no higher in this study than in routine practice. All staff administering vaccines in this study will be appropriately trained in vaccine administration and in managing any side effects from this and all vaccines will be given in an environment where emergency equipment is available.

This trial is categorised as:

- Type A = No higher than the risk of standard medical care

In the context of the current global pandemic of COVID-19 it is important that measures are taken to protect participants and staff from infection. All participating institutions should have an SOP or risk assessment for the conduct of study visits during this period and this must be available before visits recommence. If at any point a participant or a household contact of a participant is found to be experiencing any symptoms of COVID-19, the visit should not take place and they should be advised to follow the national public health guidance.

Benefit-risk assessment for trial participants in the Oxford/AstraZeneca cohort of Preg-CoV

This issue applies only to those pregnant women who have had one dose of the Oxford / Astra Zeneca (AZ) COVID-19 vaccine previously, with no serious side effects. For these individuals only, the benefits and risks of a second dose of the AZ COVID-19 vaccine will be discussed.

It is recognised that there is an increased risk of thromboembolic events with low platelets after a first (or unknown) doses of the AZ COVID-19 vaccine, with an overall incidence of 13.6 per million doses. No specific risk factors for this adverse event have been identified to this time. The incidence following a 2nd dose is reported to be 1.3 per million doses, with all cases reported being over the age of 50 years (MHRA Yellow Card reporting as of 26 May 2021).

Although pregnancy itself is associated with an increased risk of thrombosis, there is no evidence to suggest that pregnancy itself is a specific risk factor for the thromboembolic events described above. It should be acknowledged however, that there are very little data on the use of the AZ COVID-19 vaccine in pregnancy.

Conversely, there is an increased risk of severe illness from COVID-19 in pregnant women compared to non-pregnant women, particularly in the third trimester and that COVID-19 vaccines, especially 2 doses, are likely to significantly reduce this risk. Risk factors for COVID-19 in pregnancy include Black, Asian and minority ethnic background, increased BMI, pre-pregnancy co-morbidity (such as pre-existing diabetes and chronic hypertension), maternal age 35 years or older, living in areas or households of increased socioeconomic deprivation. Therefore, discussions on the benefit-risk of COVID-19 vaccines in pregnant women in general, as well of a 2nd dose of AZ vaccine, would be additionally informed by the presence or absence of these risk factors.

The following guidance from the RCOG additionally refers to statements from the JCVI and MHRA and serves as a useful text for discussions with relevant pregnant women.

RCOG (Royal College of Obstetricians and Gynaecologists) guidance (May 2021)

'If you have received a first dose of AstraZeneca vaccine, and subsequently become pregnant, you should be given the opportunity to discuss with your obstetrician, midwife or GP, your decision on whether to have your second dose. On 7 April 2021, the JCVI stated: 'To date, there are no reports of the extremely rare thrombosis/thrombocytopenia events following receipt of the second dose of the AstraZeneca COVID-19 vaccine. All those who have received a first dose of the AstraZeneca COVID-19 vaccine should continue to be offered a second dose of AstraZeneca COVID-19 vaccine, irrespective of age. The second dose will be important for longer lasting protection against COVID-19.'

Since then, there have been very rare reports of serious blood clots after a second dose of the AstraZeneca vaccine. As of 19 May 2021, 34.9 million doses of the AstraZeneca vaccine have been given in the UK. There have been 17 cases of serious blood clots following the second dose of the vaccine, compared to 315 cases after a first dose of the vaccine. The official national publication on vaccines (the Green book) advised on 7 May 2021 that: "Pfizer and Moderna vaccines are the preferred vaccines for eligible pregnant women of any age, because of more extensive experience of their use in pregnancy. Pregnant women who commenced vaccination with AstraZeneca, however, are advised to complete with the same vaccine".

Additionally, monitoring and reporting of safety events in Preg-CoV is clearly defined in Preg-CoV participant documents. Women receiving a 2nd dose of AZ will be specifically informed of the symptoms of possible thrombotic events and the need to seek urgent medical attention if any of them occur (see "What to look out for after vaccination" <https://www.gov.uk/government/publications/covid-19-vaccination-and-blood-clotting/covid-19-vaccination-and-blood-clotting>).

3 OBJECTIVES AND OUTCOME MEASURES/ENDPOINTS

3.1 Primary objective

Maternal

- To determine whether the immune response, in COVID-19 seronegative participants, to immunisation with COVID-19 vaccines according to "long" dosing intervals is superior to that observed following immunisation according to "short" dosing intervals.
- To evaluate the reactogenicity of COVID-19 vaccines, when given as 1- or 2-dose vaccination regimens, in pregnant participants.

3.2 Secondary objectives

Maternal

- To describe pregnancy outcomes in women who receive COVID-19 vaccine(s) during pregnancy.
- To evaluate safety in terms of SAEs and medically attended adverse events (MAAEs) in women who receive COVID-19 vaccines during pregnancy.
- To evaluate safety in terms of AESI (including potential immune-mediated medical conditions (PIMMCs)) relevant to COVID-19, including possible vaccine-enhanced disease, in all women at any time after the first dose of a COVID-19 vaccine.
- To evaluate the immunogenicity of COVID-19 vaccines, when given as 1- or 2-dose vaccination regimens, in serologically negative (to SARS-CoV-2) pregnant participants.
- To evaluate the immunogenicity of COVID-19 vaccines, when given as 1- or 2-dose vaccination regimens, in pregnant participants (regardless of serostatus as baseline).

Infant

- To evaluate the safety of infants born to women vaccinated with COVID-19 vaccine(s) up to 12 months after birth.
- To evaluate the transfer of SARS-CoV-2 specific antibodies from mothers vaccinated with COVID-19 vaccine(s), according to different regimens, to their infants at the time of delivery
- To evaluate the kinetics of SARS-CoV-2 specific maternal antibodies in infants born to mothers vaccinated with COVID-19 vaccine(s), up to 3 months after birth
- To assess the effect of gestational age at vaccination, interval between vaccination and delivery, maternal age, health status, vaccine type and schedule on immune responses and duration of immune responses in vaccinated women and on placental transfer and antibody kinetics in their infants

3.2.1 Exploratory objectives

Maternal

- To describe SARS-COV-2 antibodies in breast milk of mothers who receive COVID-19 vaccine in pregnancy
- To describe the effectiveness of COVID-19 vaccines in pregnancy against maternal COVID-19 in pregnancy or post-partum
- To evaluate the immunogenicity of a COVID-19 vaccine when given as a booster dose, in pregnant participants who have received one dose of a COVID-19 vaccine before pregnancy

- To compare the immunogenicity of a COVID-19 vaccine, when given as a booster dose to pregnant participants of 28-34 weeks' gestation who have received a prime dose of a COVID-19 vaccine before pregnancy, with the immunogenicity of a COVID-19 vaccine when given as a prime dose to pregnant participants of 28-34 weeks' gestation who have not received a dose of a COVID-19 vaccine previously
- To assess the impact of prime- boost interval on immunogenicity when a booster dose is given to pregnant participants of 28-34 weeks' gestation who have received a prime dose of COVID-19 vaccine before pregnancy

Infant

- To describe the effectiveness of maternal antibodies against SARS-CoV-2 to protect against COVID-19 / symptomatic disease / severity in infants in the first 12 months of life
- To describe the effectiveness of breast milk antibodies against SARS-CoV-2 to protect against COVID-19 / symptomatic disease / severity in infants in the first 12 months of life

3.3 Outcome measures/endpoints

Described in section 3.4, 3.5, 3.6.

3.4 Primary endpoint/outcome

- SARS-COV-2 IgG-specific antibody concentrations measured on blood samples collected from vaccinated maternal subjects at delivery.
- Occurrence of solicited local and general adverse events (AE) that occur during a 7-day follow-up period after each vaccination (i.e., the day of vaccination and 6 subsequent days)
- Occurrence of unsolicited AEs that occur during a 30-day follow-up period after vaccination (i.e., the day of vaccination and 29 subsequent days)

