3.7 Table of endpoints/outcomes

Objectives	Outcome Measures	Timepoint(s) of evaluation of this outcome measure (if applicable)

Primary (maternal)
 
 To determine whether the immune response, in COVID-19 seronegative participants, to immunisation with COVID-19 vaccines according to “long” dosing intervals is superior to that observed following immunisation according to “short” dosing intervals. 	
 SARS-COV-2 IgG-specific antibody concentrations measured on blood samples collected from vaccinated maternal subjects at delivery. 	
Maternal blood sampling at delivery

 To evaluate the reactogenicity of COVID-19 vaccines, when given as 1- or 2-dose vaccination regimens, in pregnant participants. 	
 Occurrence of solicited local and general adverse events (AE) that occur during a 7-day follow-up period after each vaccination (i.e., the day of vaccination and 6 subsequent days) 	
Diary data entry (solicited AE) from Day 0 to Day 6.

	
 Occurrence of unsolicited AEs that occur during a 30-day follow-up period after vaccination (i.e., the day of vaccination and 29 subsequent days) 	
Diary data entry (unsolicited AE) from Day 0 to Day 29.

Secondary Objectives Maternal
 
 To describe pregnancy outcomes in women who receive COVID-19 vaccine(s) during pregnancy. 	
 Pregnancy outcomes from Visit 1 up to 6 weeks after delivery. These include live birth with congenital anomalies, miscarriage, fetal death/still birth (antepartum or intrapartum), mode of delivery, elective/therapeutic termination. 	
Review at delivery and at 3 days, 14 days, and 42-48 days after delivery.

 To evaluate safety in terms of SAEs and medically attended adverse events (MAAEs) in women who receive COVID-19 vaccines during pregnancy. 	
 Occurrence of serious adverse events (SAEs), AEs leading to study withdrawal, and MAAEs from Visit 1 (Day 0) up to 6 weeks after delivery 	
Notification of SAE / AE / MAAE to site by participant from enrolment to 1 year after delivery / birth.

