7 TRIAL PROCEDURES

Screening + study visit 1 (Maternal)

This visit will take place between 13 0/7 – 27 6/7 gestational weeks (for the earlier gestational weeks group) or between 28 0/7 – 34 0/7 gestational weeks (for the later gestational weeks group) at the participating institution. Eligibility will be confirmed, the study will be discussed in more detail and women will be asked to sign a consent form. They will then be asked about demographic details (including NHS number), past medical history, receipt of any prior dose of a COVID-19 vaccine, details of the current pregnancy including the results of antenatal screening and scans to ensure that they are eligible for the study. The participant's antenatal medical notes will be reviewed. Details will be collected about concomitant medication. A physical examination will be performed, and vital signs, height and weight will be recorded. Immunogenicity blood samples will be obtained.

Cohort 1, 2, 3: Participants will be randomised to a single group to receive one type of COVID-19 vaccine with the first dose to be given at visit 1.

Cohort 4: Participants will receive the same vaccine as given pre-pregnancy or during their first trimester (0 0/7 – 12 6/7 gestational weeks) and randomised to either receiving the booster dose before or after 26 weeks' gestation.

Vaccination will be given by members of the study team who are trained and experienced in vaccine administration and in emergency procedures in the event of an allergic reaction. They will have access to emergency medication and equipment. The vaccinations will be given according to the advice in the “Green Book” and the Summary of Product Characteristics (SmPC). An eDiary will be set up for the participant and they will be given instructions to complete the diary regularly for 28 days following vaccination. The participant will be observed for a period of 20 minutes following vaccination to assess for allergic adverse events.

Study visit 2 (Maternal) all cohorts

14 days (10 days – 21 days) after first vaccination review by telephone call.

- SAE / AESI / MAAE check
- Concomitant medication check
- eDiary review

Study visit 3 (Maternal) all cohorts

Day 28-42 following the first vaccination at the participating institution.

- SAE / AESI / MAAE check
- Concomitant medication check
- eDiary review
- Targeted physical examination if indicated
- Immunogenicity blood samples will be collected
- **Cohort 1.**
 - Vital signs pre-vaccination

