9.3 Recording and reporting of SAEs, SARs AND SUSARs

Information about AEs and SAEs will be collected from the time of consent. Information about ARs, SARs and SUSARs will be collected from the time of administration of the vaccine. Information about SAEs will be collected for the duration of the study. Information about AEs will be enquired about at every study visit. AEs (apart from those which could reasonably be expected following vaccination- see section 9.2) will be recorded on the adverse event log for the period of 28 days following administration of the vaccine and medically attended adverse events which occur at any time in the study for the maternal participants will be collected. Medical attendance which is a routine part of antenatal care will not be considered an AE. Unscheduled medical attendances and events which meet the definition of an SAE should be recorded for the mother and infant.

Where a participant withdraws consent for further processing of data, this does not preclude the reporting of SARs and SUSARs which are required to continue being reported according to the protocol for regulatory purposes.

SAEs, SARs and SUSARs must be notified to the Sponsor immediately when the investigator becomes aware of the event (within 24 hours). Refer to JRESSOP0006 and ensure the completed SAE report form JRESDOC0012 is sent to the Sponsor by e-mail to [contact]. All sites will correspond directly with the Sponsor, copying the CI into the correspondence.

We will not require SAE reporting for women being admitted to hospital for delivery, including those women who are admitted for induction of labour and caesarean section and neither instrumental delivery nor caesarean section would be reported as an SAE although the reasons for this may be, for example, if a caesarean section took place because of a significant antepartum haemorrhage the latter would be reported as an SAE although the caesarean section would not. Whether to report complications of delivery as an SAE should be decided at the discretion of the local PI with discussion with the Sponsor and CI as necessary.

For each SAE and SUSAR the following information will be collected:

- full details in medical terms and case description
- event duration (start and end dates, if applicable)
- action taken
- outcome
- seriousness criteria
- causality (i.e. relatedness to trial drug / investigation), in the opinion of the investigator
- whether the event would be considered anticipated.

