11.1 Data collection tools and source document identification

The Chief Investigator will be responsible for all data that accrues from the study.

All study data including participant diary will be recorded directly into an EDC system (REDCap) or onto a paper source document for later entry into EDC if direct entry is not available. This includes safety, laboratory and outcome data. Any additional information that needs recording, but is not relevant for the eCRF (e.g signed consent forms) will be recorded on separate paper source documents. All documents will be stored safely and securely in confidential conditions. The EDC online data is stored on University of Oxford servers.

All participant reported adverse event data (both solicited & unsolicited) will be entered onto electronic diary cards (e-diaries) for a maximum of 28 days following administration of the IMP. The eDiary provides a full audit trail of edits and will be reviewed at time-points as indicated in the schedule of events. Any adverse event continuing beyond the period of the diary will be copied into the eCRF as required for safety review.

The participants will be identified by a unique trial specific number and code in any database. The name and any other identifying detail will NOT be included in any trial data electronic file, with the exception of the electronic diaries, for which consent will be obtained to store the participant email address for quality control purposes. Only site research staff and sponsor data managers have access to view the email address.

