16. APPENDICES

16.1 Appendix 1-Risk

Risks associated with trial interventions

A ≡ Comparable to the risk of standard medical care

B ≡ Somewhat higher than the risk of standard medical care

C ≡ Markedly higher than the risk of standard medical care

Justification: Briefly justify the risk category selected and your conclusions below (where the table is completed in detail the detail need not be repeated, however a summary should be given):

This study involves vaccinating pregnant women with COVID-19 vaccines within a time period in the UK. There is a small risk of adverse reaction to any vaccine, but this risk is low and is no higher in this study than in routine practice. All staff administering vaccines in this study will be appropriately trained in vaccine administration and in managing any side effects from this and all vaccines will be given in an environment where emergency equipment is available.

What are the key risks related to therapeutic interventions you plan to monitor in this trial?		How will these risks be minimised?		
IMP/Intervention	Body system/Hazard	Activity	Frequency	Comments
Vaccination	Adverse reaction	Post vaccination observation period to assess for adverse reactions	Post vaccination	Trained clinical research team members will be responsible for the assessments
As above	As above	Completion of eDiaries by participants post vaccination for 28 days	Daily eDiary entrees	Trained clinical research team members will be responsible for the assessments
As above	As above	Review of AE, SAE, and unscheduled medically attended AE during follow-up visits	Regular follow-up visits (up to 12 visits) during the participant's study involvement	Trained clinical research team members will be responsible for the assessments

Outline any other processes that have been put in place to mitigate risks to participant safety (e.g. DMC, independent data review, etc.)

A Data Safety Monitoring Board (DSMB) will be convened. The DSMB will evaluate frequency of events, safety and efficacy data as specified in the DSMB charter. The DSMB will make recommendations concerning the conduct, continuation or modification of the study for safety reasons to the Trial Steering Committee.

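### The primary unsolicited-AE endpoint covers Day 0–29, but five operational rules stop collection at 28 days, and its last days can overlap the Visit 3 injection

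*Protocol*

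**What the plan says.** **The endpoint.** The Trial Summary and sections 3.4 and 3.7 define the unsolicited-AE endpoint in the same way: "Occurrence of unsolicited AEs that occur during a 30-day follow-up period after vaccination (i.e., the day of vaccination and 29 subsequent days". The timepoint column of section 3.7 agrees with it: "Diary data entry (unsolicited AE) from Day 0 to Day 29".

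**The collection rules.** Five operational statements give 28 days.
- Section 7, Visit 1 (participants): "they will be given instructions to complete the diary regularly for 28 days following vaccination".
- Section 11.1 (eDiary): entries run "for a maximum of 28 days following administration of the IMP".
- Section 16.1, Appendix 1 (risk table): "Completion of eDiaries by participants post vaccination for 28 days".
- Section 9.3 (AE log): AEs "will be recorded on the adverse event log for the period of 28 days following administration of the vaccine".
- Section 9.8 repeats the 28-day limit for the AE log.

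**The next injection.** Section 7 places Visit 3 at "Day 28-42 following the first vaccination at the participating institution". At that visit the short-interval arms of cohorts 1 and 2 receive COVID-19 dose 2. Women in the cohort 1 long arm receive dTaP/IPV if they have not already had a pertussis vaccine. Women in the cohort 2 long arm may receive dTaP/IPV or nothing. Cohorts 3 and 4 are not vaccinated at Visit 3.

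**Other collection.** Section 9.3 collects SAEs for the whole study and maternal medically attended AEs at any time, and has AEs asked about at each visit. Section 10.3.3 plans counts and percentages, grouped by the schedule received.

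**The concern.** A primary endpoint needs one window, and the tools that feed it must cover that window. Here section 3.7 and section 11.1 give different limits for the same diary, and a site cannot follow both. If the diary is built to section 11.1, the endpoint is reported as 30 days although its main tools were told to stop earlier. An analysis plan cannot repair that, because it cannot recover events that nobody was asked to record.

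The end of the window also coincides with the first days on which Visit 3 may take place. Day 28 and Day 29 can be the day of another injection or the day after it. They then belong both to the dose-1 window and to the period after the next injection, and the protocol does not say where an AE on those days is tabulated.

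**Working it through.** **1. Length of the endpoint window.** Section 3.4 counts the day of vaccination plus 29 days: 1 + 29 = 30 days, Day 0 to Day 29. The stated figure reproduces. The solicited endpoint uses the same convention: 1 + 6 = 7 days, Day 0 to Day 6.

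**2. Days not covered by a 28-day tool.** The operational wording can be read in two ways.

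| Reading of 28 days | Days covered | Endpoint days left out | Share of 30 |
|---|---|---|---|
| Day of vaccination is the first day | Day 0–27 | Day 28, Day 29 | 2/30 = 6.7% |
| 28 days after the day of vaccination | Day 0–28 | Day 29 | 1/30 = 3.3% |

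The first reading follows the protocol's own convention for its endpoints. The second is possible because the operational text speaks of days following vaccination.

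**3. What is lost in those days.** SAEs and maternal medically attended AEs are collected regardless, and AESIs are checked at visits. What remains is new-onset AEs in none of these groups. Section 9.3 says AEs are asked about at each visit, but the Visit 3 procedures in section 7 list only an SAE/AESI/MAAE check and an eDiary review, and the AE log takes events for 28 days only. A Visit 3 on Day 28 also comes before Day 29. In cohorts 1–2 the next listed visit is then Visit 4, at Day 56–84.

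**4. Overlap with the next injection.** Visit 3 may fall on any of 42 − 28 + 1 = 15 days.
- Injection on Day 28: Days 28 and 29 are shared, 2 days.
- Injection on Day 29: Day 29 is shared, 1 day.
- Injection on Days 30–42: no overlap.

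Overlap therefore arises on 2 of 15 permitted days. If visits were spread evenly over the window (an assumption; the protocol gives no distribution), 2/15 = 13% of the women injected at Visit 3 would be affected, with a mean overlap of (2 + 1)/15 = 0.2 days per woman injected. Early booking would raise these figures and late booking would lower them. The long-arm COVID-19 dose at Day 56–84 cannot overlap the dose-1 window.

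**5. Does a Day 0–27 window remove both problems?** It has 1 + 27 = 28 days. It lies within the tools on either reading in step 2, and it ends the day before the earliest Visit 3 injection.

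**The case against.** The strongest reply is that this is a discrepancy of a day or two in a descriptive safety endpoint, with partial safeguards, and that attribution of events to doses is commonly settled in the analysis plan. Much of that stands. The superiority test and the sample size concern antibody at delivery and are untouched. Common reactions just after dose 2 have their own 7-day solicited endpoint, which limits what reaches the unsolicited counts.

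Three stronger readings are tempting, and the documents do not support them.
- A reader might infer that no stated tool covers the last two days. Section 3.7 does set diary entry to Day 29, so the defect is two conflicting diary lengths, and the loss depends on which one is followed.
- A reader might infer that the comparison of schedules is biased because the product given at Visit 3 differs by arm. Section 10.3.3 plans counts and percentages and states no between-schedule test of AEs. The protocol also does not say that one event is counted under two doses.
- A reader might apply the 13% to all participants. It applies at most to women in cohorts 1–2 who are actually injected at Visit 3, and only under even spacing.

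The reply does not remove the contradiction over how long participants complete the diary. That governs data collection, so it has to be settled in the protocol.

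**Conclusion.** The point holds as an internal contradiction with limited consequences. The protocol defines a primary endpoint over 30 days and in five places limits the diary or AE log to 28. If the 28-day rules are followed, new AEs that are neither serious nor medically attended go uncaptured by diary and log for 1–2 days, 3.3–6.7% of the window, depending on how 28 days is counted. Separately, a woman in cohorts 1–2 injected at Visit 3 on Day 28 or 29 has 1–2 days of overlap with the dose-1 window. How many women that concerns depends on visit timing, which the protocol does not give. The effect is confined to descriptive safety tables.

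**What to change.** Use one explicitly numbered window throughout.

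- In the Trial Summary and sections 3.4 and 3.7, define the endpoint as the day of vaccination plus 27 subsequent days (Day 0–27), and change the diary row in section 3.7 to match.
- State the same day numbering in section 7 (Visit 1), sections 9.3, 9.8 and 11.1, and Appendix 1.
- State that if a further COVID-19 dose falls inside a window, AEs starting on or after that dose are tabulated under it.
- Do not end the window at dTaP/IPV. In cohorts 2–4 that vaccine may be given as little as one week from a COVID-19 dose (notes to Tables 2–4), so such a rule could cut some windows to about 7 days.

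The cost is rewording and a safety window two days shorter (28 instead of 30). Extending the 28-day rules to Day 29 would also end the contradiction, but it would lengthen diary and log collection and leave the overlap at Days 28–29 in place. Neither route implies any change to the vaccination schedule.
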